### 1.2 Secondary Objectives

- 1.2.1 To estimate the efficacy of a tDCS intervention paired with cognitive stimulation.

Hypothesis 2: The home-based tDCS and cognitive training intervention will result in improved executive function in adult survivors of childhood after a five week intervention.

- 1.2.2 To explore the short-term effect of tDCS on measures of executive function among adult survivors of childhood ALL participating in the SJLIFE study.

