### 2.2 Rationale:

Cognitive training has been used in an attempt to improve neurocognitive impairment in cancer survivors. We recently completed a pilot study of a cognitive stimulation trial to improve function in adult survivors of childhood cancer. Twenty-one survivors completed six months of regular cognitive exercises, with pre- and post-neurocognitive testing. Compared to an equated

reference group tested at a similar interval, those who completed training exercises demonstrated significant improvement in cognitive flexibility and processing speed. However, the effect sizes were relatively small and, given the long-standing nature of the impairment, extended training, more intensive training, or an additional intervention to support the training may be necessary to enhance effects.

A potentially useful tool to enhance cognitive intervention is transcranial Direct Current Stimulation (tDCS). tDCS involves modulation of cerebral cortex excitability by the application of weak direct current to the scalp. tDCS is a technique that applies safe, low level direct current through large pads on the scalp to stimulate the underlying brain region, with current level < 0.10 C/cm^2 (as a reference, tissue damage occurs at levels of ~ 200 C/cm^2 or higher). The schematic below demonstrates the manner in which the tDCS intervention is delivered to the participants.

A cross-over study of tDCS on working memory using healthy volunteers showed that tDCS modulated working memory performance (measured by letter n-back) by altering dorsolateral prefrontal cortex (DLPFC) brain activity in a polarity-specific way, in that anodal tDCS enhanced the performance related to working memory. Another study in healthy volunteers found that anodal tDCS of DLPFC or the primary motor cortex (M1) increased performance on a cognitive or motor task, respectively.

tDCS is also a safe method for enhancing cortical responsivity. A recent meta-analysis looked at over 200 studies for adverse events (AE) related to active

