### **5.2.3 Woodcock Johnson Understanding Directions**

The Woodcock Johnson Understanding Directions is a measure of listening comprehension. The task requires the participant to listen to a series of complex instructions and then follow the directions by pointing to various objects in a colored picture. Directions require sequential and logical reasoning, components of executive function. Four complex instructions will be administered each day, from alternate test forms, and raw scores will be calculated and compared within participants. Total testing time will be approximately 5 minutes after each clinical tDCS session.

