### **5.2.4 Remote Assessment Procedures**

We have recently completed a pilot study to evaluate the accuracy of remote cognitive assessment, using web and phone based procedures. We will employ these procedures prior to

and following the initiation of phase II of the trial. Specifically, the following tests will be administered:

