### **Analysis:**

Objective 1.1.1: The feasibility of the 5-week tDCS intervention will be evaluated using Simon's two stage Minimax design with stopping rules described above.

Objective 1.2.1: The improvement in scores on symbol digit coding, Stroop test, shifting attention test, digit span and verbal fluency from baseline to 5-week follow up will be done using matched pair one sample t-tests. In addition, the improvement in EF measures over the 5 week period will also be evaluated using longitudinal methods and implemented using PROC MIXED or PROC GEE in SAS 9.3.

Objective 1.2.2: The improvement in the scores on the NIH Toolbox Card Sort, Flanker and Working Memory tasks between tDCS and sham, will be done using matched pair one sample t-test.

It will be important to monitor for AEs in both phases of the study as well. Thus, in an "ad hoc" manner using one sided 95% confidence bounds we will monitor for all grade 3 or higher adverse events (All types of AE's included)

which are related to study interventions. Among the 45 patients enrolled in the study, if at any time point at least 5 patients ( $\geq 5$ ) have grade 3 or higher toxicity, the 95% lower confidence limit would be 0.059 suggesting that the true AE rate could be higher than 5% which would be unacceptable, the feasibility of the 5 week intervention would be questionable and a consideration will be given to stop or amend the trial.

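### Objective 1.2.1 tests pre/post change in a single treated group against zero, so a retest gain would be read as support for Hypothesis 2

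*Combined protocol and SAP*

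**What the plan says.** Section 1.2 words the objective as estimation: "To estimate the efficacy of a tDCS intervention paired with cognitive stimulation". The hypothesis attached to it is causal: "The home-based tDCS and cognitive training intervention will result in improved executive function".

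Section 9 (Analysis, Objective 1.2.1) assesses five scores, with improvement "from baseline to 5-week follow up will be done using matched pair one sample t-tests". It adds that "the improvement in EF measures over the 5 week period will also be evaluated using longitudinal methods", using PROC MIXED or PROC GEE, but names no comparator there either. The power statement gives roughly 97.7% for an improvement of 0.65 standardised units with 37 survivors and type I error 0.05.

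Phase II has one arm. Section 4.2.2 gives every participant active 1 mA sessions; sham appears only in the two-day Phase I cross-over (Sections 4.1 and 4.2.1). Remote testing is done before and after Phase II (Sections 4.1 and 5.2.4).

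Two safeguards against retest gain appear elsewhere in the document. In the earlier cognitive training pilot (Section 2.2), results were read against an equated "reference group tested at a similar interval, those who completed training exercises demonstrated significant improvement". In Phase I, the reading test alternates Form A and Form B (Section 5.2.2), and for the listening test "Four complex instructions will be administered each day, from alternate test forms" (Section 5.2.3). Section 5.2.4 states no forms for the Phase II tests.

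**The concern.** People often score better on a cognitive test the second time they take it. A one-sample test of change against zero cannot separate that gain from an effect of stimulation and training. Because everyone in Phase II is treated, nothing else in the planned analysis separates them. The longitudinal model describes the same within-group change and has the same limit.

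What is at stake is the reading of Hypothesis 2. A significant t-test would show that scores rose. It would not show, at a 5% error rate, that the intervention raised them.

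**Working it through.** **1. The plan's own figure.** Inputs from Section 9: n = 37, standardised improvement 0.65, alpha 0.05 (sidedness not stated).

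- Normal approximation, two-sided: Φ(0.65 × √37 − 1.96) = Φ(3.954 − 1.960) = 0.977. This matches the stated 97.7%.
- Noncentral t, two-sided: 0.970.

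The power arithmetic is sound. The zero null is not written out. It is implied by a paired test of improvement and by a power figure that reproduces when the whole 0.65 is counted as distance from the null.

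**2. The change that reaches significance.** The two-sided 5% critical value of t on 36 degrees of freedom is 2.028. Dividing by √37 = 6.083 gives 0.333. An observed mean gain of about 0.33 SD of the change score is therefore significant, whatever caused it.

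**3. Retest gain only, no intervention effect.** The documents give neither of the two inputs needed, so both are assumptions:

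- retest gain g = 0.1 to 0.3 SD of the score;
- pre/post correlation r = 0.5 to 0.8.

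With equal SDs before and after, the standardised change is d = g / √(2(1 − r)). For example, g = 0.1 and r = 0.5 give 0.1 / 1 = 0.100; g = 0.3 and r = 0.8 give 0.3 / 0.632 = 0.474. The chance of a significant result in the direction of improvement follows from the noncentral t distribution with noncentrality d√n. With no gain it is 2.5%.

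| r | g | d | n = 37 | n = 30 |
|---|---|---|---|---|
| 0.5 | 0.1 | 0.100 | 8.6% | 7.6% |
| 0.5 | 0.3 | 0.300 | 42.7% | 35.5% |
| 0.7 | 0.1 | 0.129 | 11.6% | 10.1% |
| 0.7 | 0.3 | 0.387 | 63.0% | 53.6% |
| 0.8 | 0.1 | 0.158 | 15.3% | 13.1% |
| 0.8 | 0.3 | 0.474 | 80.2% | 70.9% |

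The n = 30 column is illustrative, for the case where fewer than 37 provide both assessments. These are rates per outcome, and Section 9 tests five.

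**4. Which tests, and from when.** Of the five outcomes in Section 9, only digit span and verbal fluency are clearly in the remote battery of Section 5.2.4. Symbol digit coding, Stroop and shifting attention are not listed there. Baseline could mean the pre-Phase II remote session or the SJLIFE testing, which Section 5.1.1 calls the baseline evaluation. On the SJLIFE reading the interval would no longer be 5 weeks. Because low SJLIFE scores are part of eligibility (Sections 3.1.5 and 5.1.1), regression to the mean could then add to any retest gain.

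**The case against.** The strongest reply is that this is a pilot. The objective is secondary and worded as estimation, the overview speaks of potential efficacy, and Section 9 foresees a later randomised controlled trial. An uncontrolled pre/post estimate is an ordinary limit of such a study. That stands and sets the severity. It does not remove the mismatch between a causal hypothesis, supported by a t-test, an alpha and a power figure, and a design that cannot isolate the cause.

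The size of the problem is also uncertain. Both inputs are assumed, and 80% is the extreme corner of the grid. Digit span and verbal fluency were already taken at SJLIFE, so the pre-Phase II session is not a first exposure and the further gain may be smaller. The absence of alternate forms is inferred from silence: Section 5.2.4 relies on procedures from elsewhere ("We have recently completed a pilot study to evaluate the accuracy of remote cognitive assessment"), and those are not in the documents. All of this stands.

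Three stronger readings are tempting but not supported:

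- **That a false positive would justify or size the later trial.** Section 9 ties that trial to feasibility, with rules on session completion and consent rate. Nothing uses the 1.2.1 result to start or size it, and there is no written acceptance rule for Hypothesis 2.
- **That the earlier pilot's effects are of a size that retest gain would imitate.** Section 2.2 calls them relatively small but gives no figure. They were measured relative to a reference group, after six months of training.
- **That the test against zero should be replaced by a test against a retest benchmark.** The documents do not show that retest data exist for these tests or for a 5-week interval. If 0.65 is total change, a fixed benchmark of 0.129 to 0.474 SD of change leaves power of about 87% down to 18% at n = 37.

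**Conclusion.** The point holds as a minor one. The planned test of objective 1.2.1 can establish change in treated participants but cannot support the causal wording of Hypothesis 2 at the nominal error rate. The direction is certain for any positive retest gain; the size is not. Under a gain of 0.1 to 0.3 SD and a correlation of 0.5 to 0.8, both assumed, significant improvement with no intervention effect would occur about 9% to 80% of the time per outcome at n = 37, against 2.5% with no gain. The 97.7% power figure is correct for the test as planned. The primary feasibility objective and its two-stage rule are unaffected.

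**What to change.** 1. **Section 5.2.4.** Use alternate forms before and after Phase II where they exist, at least different letter sets for Verbal Fluency, with the order counterbalanced across participants. This extends what Phase I already does for its reading and listening tests. It reduces gains tied to specific items but not general familiarity with testing.
2. **Section 9.** State that baseline is the pre-Phase II remote assessment. Report objective 1.2.1 as uncontrolled change in treated participants with a 95% CI, and state that a significant t-test against zero will not be used to accept Hypothesis 2. Apply the same wording to the longitudinal analysis. Reconcile the outcome list with the Section 5.2.4 battery so that it is clear which scores this covers.
3. **Optional sensitivity analysis.** If the earlier training pilot gave its reference group the same tests, compare the observed change with that group's retest change. Note that the earlier training ran for six months with a similar retest interval, so its retest gain may not match that at 5 weeks.

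The cost is wording in two sections and the preparation of forms, with no extra visits or participants. The downsides are a more modest efficacy statement and slight form-to-form variability in the change scores.

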## 4 DESIGN AND METHODS

### 4.1 DESIGN AND STUDY OVERVIEW

The proposed study will be conducted in two phases. In Phase I, the short-term effect of tDCS on performance on measures of executive function will be evaluated over a two-day period. After assessing the effect in Phase I, and providing participants with a directly observed experience with tDCS, the feasibility of self-administering tDCS over long-term (5 weeks with two sessions per week) using a mobile tDCS device and its potential efficacy will be evaluated in Phase II. The 5-week intervention will be paired with cognitive stimulation using the Lumosity Brain Games program ([www.lumosity.com](http://www.lumosity.com)). This program involves cognitive exercises designed to enhance executive function and processing speed, to be performed on an institutionally provided iPad. Cognitive stimulation activities can be completed in 15-20 minutes per session. The study schema is displayed in the Figure below:

Figure 1. ALLSTIM Study Schema

A cross-over randomized trial will be used in Phase I. The survivors will be randomized to receive either the tDCS intervention at the current dose level of 1mA or Sham for 15 minutes on day 1 and then on day 2 the other treatment will be provided (i.e. those who got tDCS intervention of day 1 will get sham on day 2 and vice versa). The tDCS intervention will be delivered by the Soterix Transcranial Direct Current Stimulator Clinical Trials (1x1-CT). The effect of one session to tDCS is expected to last for about two hours thus conducting the second session the next day will provide sufficient time for the “wash-out” and good justification for using a cross-over design.

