## 4.2 STUDY PROCEDURES:

### 4.2.1 Transcranial Direct Current Stimulation – Clinical System

The system used for stimulation is the Transcranial Electrical Stimulation 1x1 Clinical Trials Device manufactured by Soterix Medical. This system allows for double-blinded application of the intervention or sham treatment. The intervention consists of a direct current of 1 mA applied for 15

minutes. The sham procedure provides the same small current during ramp up to imitate the intervention, but the current is discontinued after ramp up and no intervention is provided.

Direct current is transferred by a pair of saline-soaked sponges, with the anode attached to the left frontal region (F3) and the cathode attached over the right eyebrow (Fp2). Participants will be randomized to receive the intervention on day 1 and the sham on day 2 or vice versa. Within two hour of completing the intervention and sham, participants will complete the NIH Toolbox Cognitive Battery on both days.

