## 5.2 Evaluations During Therapy

### 5.2.1 NIH Toolbox – Cognitive Battery

We will use the three tests from the Cognitive Battery of the NIH Toolbox to evaluate the acute effect of tDCS on executive function. These three measures have a computerized format and are nationally standardized. Testing will occur post-intervention (total 2 times) during phase I.

NIH Toolbox Dimensional Change Card Sort Test (DCCS): The DCCS specifically taps cognitive flexibility, with performance generally increasing through childhood and then declining across the adult age. A total of 40 trials require 4 minutes. Scoring is based on a combination of accuracy and reaction time. This combination score is then converted to a scale score with mean of 100 and SD of 15, where higher scores indicate higher levels of cognitive flexibility.

NIH Toolbox Flanker Inhibitory Control and Attention Test: The Flanker taps inhibitory control and attention, the capacity for new learning and information processing in novel situations – measure, in which performance reaches a peak in early adulthood, and then tends to decline across the life span. A total of 40 trials require 4 minutes. Scoring is based on a combination of accuracy and reaction time, this combination score is then converted to a scale score with mean of 100 and

SD of 15, where higher scores indicate higher executive function.

NIH Toolbox List Sorting Working Memory Test: List Sorting is tapping both information processing and storage, with performance tending to peak in early adulthood and then declining across the life span. The raw score obtained is converted to Age-Adjusted to the national norms. Higher scores on each of these indicate higher levels of working memory. This task assesses working memory and requires the participant to sequence different visually- and orally-presented stimuli. The list scoring task takes approximately 7 minutes to administer. List Sorting is scored by summing the total number of items correctly recalled and sequenced on Lists-1 and -2, which can range from 0-26.

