### **5.2.2 Gray Oral Reading Test**

The Gray Oral Reading Test (GORT) will be used to measure reading comprehension. The GORT is one of the most widely used measures of oral reading fluency and comprehension in the United States. Participants will be asked to read a set of passages and recall specific details from the stories. Responses to the test require literal as well as inferential comprehension, the latter of which involves executive function. Two stories will be given each day, one day from Form A and one day from Form B. Raw scores will be calculated for total accuracy, and compared within participants. Total testing time will be approximately 5 minutes after each clinical tDCS session.

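### Objective 1.2.2 analyses the randomised tDCS/sham crossover with a paired t-test and no day term, so a day-2 practice gain widens the standard error and, if the realised sequences are unequal, shifts the estimate

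*Combined protocol and SAP*

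**What the plan says.** Section 1.2 lists Objective 1.2.2 among the secondary objectives and words it as exploratory: "To explore the short-term effect of tDCS on measures of executive function". The design is a two-sequence crossover. Section 4.2.1: "Participants will be randomized to receive the intervention on day 1 and the sham on day 2 or vice versa". Neither the overview nor Sections 4.1, 4.2.1 and 9 give an allocation ratio, blocking or any other rule to keep the sequences equal.

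The Toolbox tasks are given once per day, after stimulation only. Section 5.2.1: "Testing will occur post-intervention (total 2 times) during phase I". No baseline or practice administration is described for Phase I.

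Under Analysis in Section 9, the comparison "between tDCS and sham, will be done using matched pair one sample t-test". The mixed-model and GEE methods in the same section are named only for Objective 1.2.1. On the spacing of the two sessions, Section 4.1 argues that "conducting the second session the next day will provide sufficient time for the" wash-out of a stimulation effect expected to last about two hours.

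**The concern.** Someone who takes the same tasks on two successive days may do better the second time, whatever the stimulation. In the tDCS-first sequence that gain counts against tDCS; in the sham-first sequence it counts in favour. A one-sample test on the pooled differences cannot tell this from random variation between participants. With nearly equal sequences the result is a standard error that is too large. With unequal sequences the estimate itself also moves.

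The wash-out argument does not answer this. It concerns carry-over of stimulation, not improvement from repetition.

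Phase II has no sham arm, so Phase I supplies the study's only randomised, sham-controlled evidence on tDCS, in a pilot meant to lead to a randomised trial. A real short-term effect could be missed, or its size misjudged, because of a nuisance effect that the randomised sequence allows the analysis to remove.

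**Working it through.** **The plan's own power figure.** Section 9 gives 97.7% power for 37 participants, a standardised effect of 0.65 and alpha 0.05. It is stated for Objective 1.2.1; there is no figure for 1.2.2. The two-sided normal approximation gives Φ(0.65 × √37 − 1.96) = Φ(1.994) = 97.7%, so it reproduces. The exact t calculation gives 97.0%.

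**Model.** Let D be a participant's tDCS-minus-sham difference, τ the true effect and π the day-2 gain.
- tDCS first: D = τ − π + error.
- Sham first: D = τ + π + error.

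With a tDCS-first and b sham-first participants (n = a + b):
- bias of the pooled mean = π(b − a)/n;
- near balance, the variance of D is inflated by about π²/sd², where sd is the within-sequence SD of D;
- the day-adjusted estimate is the average of the two sequence means, with standard error (sd/2)√(1/a + 1/b) and n − 2 degrees of freedom. It does not depend on π.

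**Inputs.** n = 37 is from Section 9. The SD of 15 is from Section 5.2.1, stated there for the Card Sort and Flanker tests. Assumed, because the documents give neither: retest correlation r = 0.7 to 0.8 and π = 3 to 7.5 points. Then sd = 15√(2(1 − r)) = 11.62 (r = 0.7) or 9.49 (r = 0.8).

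**Near balance.** Simulated, two-sided 0.05, true effect 0.5 sd in favour of tDCS for the power columns; splits are tDCS-first/sham-first.

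| r | π | Variance inflation | SE too wide by | Size, 19/18 | Paired power, 19/18 | Paired power, 18/19 |
|---|---|---|---|---|---|---|
| 0.7 | 3 | 7% | 3% | 4.3% | 81.5% | 83.5% |
| 0.7 | 5 | 19% | 9% | 3.4% | 77.3% | 81.3% |
| 0.7 | 7.5 | 42% | 19% | 2.0% | 69.4% | 76.4% |
| 0.8 | 3 | 10% | 5% | 4.1% | 80.2% | 83.1% |
| 0.8 | 5 | 28% | 13% | 2.8% | 74.1% | 79.4% |
| 0.8 | 7.5 | 63% | 27% | 1.4% | 62.3% | 71.5% |

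With a day term, power is 84% in every row. At an effect of 0.65 sd, the paired test has 96% down to 88% power (19/18) or 97% down to 93% (18/19), against 97% adjusted.

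**Unequal sequences.** At 19:18 the bias is π/37, or 0.08 to 0.20 points, which is negligible. At 22:15 it is 7π/37, or 0.57 to 1.42 points. An effect of 0.5 sd is 5.8 points (r = 0.7) or 4.7 points (r = 0.8), so the bias runs from 0.57/5.8 = 10% to 1.42/4.7 = 30% of it.
- 22 tDCS-first, 15 sham-first: the estimate is pulled down and power falls to between 74% and 34%.
- 15 tDCS-first, 22 sham-first: the estimate is pushed up and power is 89% to 91%.
- Type I error is 5.2% to 5.7% either way.
- With a day term: no bias, and 83% power.

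Under simple 1:1 randomisation of 37, a split at least as uneven as 22:15 has probability 0.324.

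**Averaged over simple 1:1 randomisation.** The paired test is unbiased with size about 5%, but its power at 0.5 sd is 82% down to 64%, against 83% adjusted.

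**No day effect (π = 0).** At 0.5 sd, the day term costs 0.1 percentage points of power at 19:18 and 1.4 at 22:15 (84.1% to 82.7%).

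**The case against.** The strongest reply is that randomised sequence already makes the planned test valid: averaged over the randomisation it is unbiased with size about 5%, and near balance it errs on the safe side. That is correct. The bias is conditional on the split that occurs. But that split produces the one estimate the study will report, and the power loss remains after averaging.

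The practice gain and retest correlation are assumptions without support in the documents. This stands too. The large losses need the top corner of the range: half an SD gained overnight with a correlation of 0.8. At the bottom corner the loss is 1 to 3 points of power, and with no gain there is none.

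More than 37 may complete Phase I, since Section 9 plans for 45 and stops accrual when 37 agree to Phase II. At 45 (23:22) the paired test has about 89% power at 0.5 sd in the low corner and 74% in the high corner, against about 91% adjusted. The pattern is the same; 37 is the plan's own Phase I figure.

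Alternate forms might limit practice, but the protocol describes them only for the reading test ("Two stories will be given each day, one day from Form A and one day from Form B") and the listening test ("Four complex instructions will be administered each day, from alternate test forms"), not for the three Toolbox tasks analysed here.

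Finally, the objective has no hypothesis, power target or decision rule. That limits the consequence but does not justify leaving out a term that costs almost nothing near balance.

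**Conclusion.** The concern holds. That the planned test leaves a day effect in the error variance, and in the estimate when sequences are unequal, follows from the stated design and needs no assumption. How much it matters depends on a practice gain the documents do not give. With a gain of 3 to 7.5 points and n = 37, the consequences range from slight to a loss of about 22 points of power at a 19:18 split (84% to 62%). At 22:15 there is also a shift of 0.6 to 1.4 points, in a direction set by which sequence is larger.

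The effect is confined to an exploratory secondary objective. The two-stage feasibility design and its decision rules are unaffected, and the plan's 97.7% power figure is not in dispute. This should be corrected, but it does not threaten the main purpose of the trial.

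**What to change.** In Section 9, replace the paired t-test for Objective 1.2.2 with the standard 2x2 crossover analysis: treatment and day as fixed effects, participant as a random effect. Equivalently, compare the day-2-minus-day-1 differences between the two sequences with a two-sample t-test and halve the result. The mean difference is τ + π in the sham-first sequence and π − τ in the tDCS-first sequence, so subtracting gives 2τ and the day gain drops out.

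The change is one sentence and one degree of freedom, with no new data. If there is no day effect, the price at 0.5 sd is 0.1 points of power at 19:18 and 1.4 at 22:15. It rises to 2.3 at 23:14, 3.5 at 24:13 and 5.1 at 25:12; splits at least that uneven have probability 19%, 10% and 5% under simple 1:1 randomisation. Those are also the splits at which the paired test would be most biased if a day effect exists.
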